### III. Analysis

#### A. Study Statistics

1. Primary outcome variable
  - a) Questionnaire ratings before and after treatments
    - (1) Neck Disability Index (Appendix E) [28-31]
    - (2) SF-12 Health Survey (Appendix F) [32]
    - (3) Visual Pain Analog (Appendix C) [33]
2. Statistical plan including sample size justification and interim data analysis
  - a) Paired T-tests (N~10 subjects) to investigate the changes in neck pain after each treatment protocol.
  - b) One-Way ANOVA to investigate any statistically significant differences between the means of each of the 4 experimental groups.
3. Early stopping rules

- a) Any adverse effect, as determined by the attending licensed osteopathic physician. No adverse effects are anticipated.
- B. Blinding
  - 1. All outcome analyses will be performed in a blinded fashion. Subject survey and corresponding data will be de-identified and analyzed retrospectively by investigators with no exposure to the treatment sessions. Doing so will eliminate bias associated with investigator self-interest and ensure subject anonymity.

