**Research Purpose:**

The purpose of this project is to investigate the individual and combined effects of Osteopathic Manipulative Treatment (OMT) and Bio Electro-Magnetic Energy Regulation (BEMER) Therapy on neck pain in adults.

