  - b) Each subject in the OMT groups (i.e. OMT and OMT+BEMER) will receive treatment 3 times per week for a period of 3 weeks. As previously mentioned, subjects in the BEMER groups (i.e. BEMER and OMT+BEMER) will receive treatment 5 times per week for a period of 3 weeks. Finally, subjects in the Placebo group will receive the combined light touch and BEMER sham treatments at same intervals as the corresponding experimental groups. OMT, BEMER, and placebo treatments will be performed by osteopathic medical students who have completed additional training given by a licensed osteopathic physician, to ensure uniform technique. All treatments will be performed during the span of three consecutive weeks.
  - c) Subjects will complete brief questionnaires regarding neck pain and quality of life before the beginning of study and will complete the same questionnaires following the completion of the three week treatment (Appendices C, E, F).

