#### I. Inclusion

A. LECOM-Bradenton faculty, staff and Students currently enrolled in LECOM-Bradenton's osteopathic medical program, pharmacy program, dental program, and master's program who are currently experiencing neck pain will be approached for recruitment.

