#### Section 1: Pain Intensity

- = I have no pain at the moment
- = The pain is very mild at the moment
- = The pain is moderate at the moment
- = The pain is fairly severe at the moment
- = The pain is very severe at the moment
- = The pain is the worst imaginable at the moment

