| 6. Accomplished less than you would like                    |  |  |
| 7. Didn't do work or other activities as carefully as usual |  |  |

8. During the past 4 weeks, how much did pain interfere with your normal work (including both work outside the home and housework)?

- |                          |                          |                          |                          |                          |
|--------------------------|--------------------------|--------------------------|--------------------------|--------------------------|
|  |
| Not at all        | A little bit      | Moderately        | Quite a bit       | Extremely         |

These questions are about how you feel and how things have been with you during the past 4 weeks. For each question, please give the one answer that comes closest to the way you have been feeling. How much of the time during the past 4 weeks –

	All of the Time	Most of the Time	A Good Bit of the Time	Some of the Time	A Little of the Time	None of the Time
9. Have you felt calm and peaceful?						
10. Did you have a lot of energy?						
11. Have you felt downhearted and blue?						
12. During the past 4 weeks , how much of the time has your physical health or emotional problems interfered with your social activities (like visiting with friends, relatives, etc.)?						
	All of the time	Most of the time	A Good Bit of the time	Some of the time	A little of the time	None the time

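### Three unranked instruments share the primary outcome, and the only between-arm test, an omnibus ANOVA, is tied to no instrument, score, contrast, significance level or multiplicity rule

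*Combined protocol and SAP*

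**What the plan says.** Section III.A.1 has one heading, in the singular, for the primary outcome variable. The entry under it is "Questionnaire ratings before and after treatments", followed by the NDI, the SF-12 and the pain VAS. None is ranked above another, and there are no secondary outcomes.

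Section III.A.2 contains the whole analysis plan, in two lines:

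- "Paired T-tests (N~10 subjects) to investigate the changes in neck pain after each treatment protocol"
- "One-Way ANOVA to investigate any statistically significant differences between the means of each of the 4 experimental groups"

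The Research Purpose is to "investigate the individual and combined effects of Osteopathic Manipulative Treatment (OMT") and BEMER therapy. Section I.F describes the combined light-touch and sham-BEMER arm as the control. Under Experimental Sessions, "Subjects will complete brief questionnaires regarding neck pain and quality of life before the beginning of study", and the same forms are repeated after the three weeks, so each subject has a baseline and a post-treatment score on every instrument. The inclusion criterion is that faculty, staff and students "who are currently experiencing neck pain will be approached for recruitment".

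The documents give no significance level, sidedness, multiplicity rule, planned contrast or rule for success.

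**The concern.** Four things are left open, and together they decide what a positive result would mean.

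1. **Which instrument counts.** With three instruments of equal rank, the plan does not say whether one or all must succeed, or which prevails if they disagree. If any one suffices, the false-positive risk exceeds that of a single test. If all three are required, it does not, but power is lost.
2. **What the ANOVA compares.** The line names no instrument and does not say whether the means are post-treatment scores or changes.
3. **Which comparison answers the aim.** A significant omnibus F says only that some means differ. It does not say that an active arm beat placebo, or that the combination beat either component. It cannot by itself answer a question about individual and combined effects.
4. **What the paired tests may support.** Subjects enter while in pain, so scores may improve in every arm, placebo included. A significant change within an active arm could then be read as a treatment effect when placebo changed as much.

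**Working it through.** **Inputs from the documents.** Four arms (section I.C); three instruments (III.A.1); about 10 subjects per paired test (III.A.2), read as per arm. This agrees with the budget: 4 x 10 = 40, and $2,000 / $50 = 40. The figure of 10 cannot be derived, because no level, power, effect size or SD is given.

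**Assumptions.** Two-sided 0.05 per test, equal allocation, normally distributed change scores, and pairwise correlation between instruments from 0 to 0.9. Some correlation is likely: the NDI opens with "Section 1: Pain Intensity", and SF-12 item 8 asks "how much did pain interfere with your normal work".

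**Step 1. Three ANOVAs, no true effect.** If the instruments were independent, the chance of at least one false positive is 1 - (1 - 0.05)^3 = 1 - 0.857 = 0.143. Simulation (100,000 trials per setting, 4 x 10) gives, by correlation:

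| Rule for success | 0 | 0.5 | 0.9 |
|---|---|---|---|
| Any one of three ANOVAs | 0.14 | 0.13 | 0.09 |
| All three ANOVAs | 0.0001 | 0.002 | 0.02 |
| Any ANOVA, or active-arm paired improvement on NDI or VAS | 0.24 | 0.21 | 0.16 |
| Any ANOVA, or active-arm paired improvement on any of the three | 0.28 | 0.25 | 0.17-0.18 |

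The third row takes neck pain to exclude the SF-12; the fourth includes it. The any-one-ANOVA risk depends on the assumed level: about 2-3% at 0.01 and 16-27% at 0.10.

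**Step 2. Paired tests when every arm improves equally.** Let d be the mean improvement in units of the SD of change, the same in all four arms, so no treatment beats placebo. The chance p that one arm of 10 shows a significant improvement is the probability that a noncentral t (9 df, noncentrality d x sqrt(10)) exceeds 2.262. The arms are independent, so:

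- at least one of three active arms significant: 1 - (1 - p)^3
- at least one active arm significant and placebo not: [1 - (1 - p)^3] x (1 - p)

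| d (assumed) | p | Any active arm | Any active arm, placebo not |
|---|---|---|---|
| 0.2 | 0.082 | 1 - 0.918^3 = 0.23 | 0.226 x 0.918 = 0.21 |
| 0.5 | 0.293 | 1 - 0.707^3 = 0.65 | 0.646 x 0.707 = 0.46 |
| 0.8 | 0.616 | 1 - 0.384^3 = 0.94 | 0.943 x 0.384 = 0.36 |

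This is for one instrument, so it is separate from the multiplicity in Step 1.

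**Step 3. Power with a baseline-adjusted contrast.** Assume 0.8 SD benefit in every active arm, 10 per arm, and pre/post correlation 0.5. The standard error of an active-minus-placebo difference is about sqrt(1 - 0.5^2) x sqrt(2/10) = 0.866 x 0.447 = 0.387 SD, and 0.8 / 0.387 = 2.07 against a critical value of 2.03 (35 df). Simulated power per contrast is 51% unadjusted and 39% with Holm over three contrasts. If only one arm works, its power with Holm is about 33%.

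**The case against.** The strongest reply is that the plan does have a between-group test. The ANOVA is its only between-arm analysis and so the natural basis for a conclusion, while the paired tests are there only to look at change, with no claim of superiority attached. This stands in part. A reader might infer that the plan has no between-arm test at all; the ANOVA line shows otherwise. What is missing is its designation as deciding, its instrument and score, and its contrasts.

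The error rates also invite stronger readings than the text allows:

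- **Fifteen tests.** Counting 12 paired tests (4 arms x 3 instruments) plus three ANOVAs gives a 31-47% chance that something is significant. The plan limits the paired tests to neck pain, and Experimental Sessions separates neck pain from quality of life, so the SF-12 may not be tested that way. The figure also counts change in the placebo arm and worsening, which nobody would claim as efficacy. It is not the false-positive rate of a primary claim.
- **Paired tests as false claims.** The 23%, 65% and 94% in Step 2 include trials in which placebo is significant too, which would expose the misreading. The frankly misleading pattern occurs in 21%, 46% and 36%.
- **An any-one rule.** The plan does not adopt one. It adopts no rule.

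Finally, the study is small and its purpose is worded as investigation. But the documents do not call it a pilot or exploratory; they declare a primary outcome and look for statistical significance, so size does not excuse the silence.

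**Conclusion.** The concern holds in this form: three unranked primary instruments, no success rule, level or adjustment, and an omnibus ANOVA that is not specified well enough to answer the stated aim. Under the assumptions above, the false-positive risk runs from about 0.01-2% if all three ANOVAs must succeed, through 9-14% if any one may be claimed, to 16-24% (17-28% with the SF-12) if an active-arm paired improvement may also be claimed. The same data could be called positive or negative depending on a rule chosen afterwards. The within-arm problem needs no multiplicity argument: paired tests use no control data and cannot show benefit over placebo.

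The level, the correlations and the shared improvements of 0.2 to 0.8 SD are assumptions, because the documents give none. The percentages are illustrative; the omissions are not. The plan should be changed before any data are seen.

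**What to change.** Before any data are seen:

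1. Name one primary instrument and one score from it, chosen by the sponsor. Make the other two secondary.
2. Make the primary analysis between-arm at two-sided 0.05, on the post-treatment score adjusted for its baseline. Name the contrasts, for example each active arm versus placebo, and state a familywise adjustment such as Holm.
3. Treat the four-group F test as supportive. Report the combination versus each single treatment as a secondary estimate with a 95% confidence interval.
4. Report within-arm changes descriptively, as mean change with a 95% confidence interval.
5. If all three instruments stay primary, state whether one or all must succeed. If any one suffices, adjust across all instrument-by-contrast tests (3 x 3 = 9 in the example), not only within each instrument.

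Holm and baseline adjustment are sound choices, not the only ones. An estimation-based plan openly labelled exploratory would also close the gap, provided the document says so.

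**Cost.** A few lines of text, with no extra subjects or visits, since both scores are already collected. The price is power: in the Step 3 example, 51% per contrast unadjusted becomes 39% with Holm over three contrasts (about 33% if only one arm works) and about 25% with Holm over nine.

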position and then rotate the head and neck to one side. This position will be held for 30 seconds. If at any time the subject complains of dizziness, visual changes, lightheadedness and/or the evaluating student notes eye nystagmus then this is considered a positive test. A positive test will exclude the subject from the study. The test is performed bilaterally [27].

E. Bio Electro-Magnetic Energy Regulation (BEMER)

1. Protocol

a) Subject will lay supine on the BEMER mat, and place the B.Pad® on their cervical neck. BEMER mat intensity 3 will be selected in week 1, intensity 4 for week 2, and intensity 5 for week 3. B.Pad® will be set at Program 1 for the duration of the intervention. Treatments last approximately 15-25 minutes.

2. Explanation of BEMER

a) BEMER is a therapeutic modality that deploys a biorhythmically defined stimulus through Pulsed Electromagnetic Field (PEMF). This stimulus has a targeted effect on the microvasculature, and the primary effect is an improvement in tissue microcirculation [9]. The positive effects of vasomotion (i.e. opening of the blood vessels) on the microcirculation has been shown to result in significant increases in arteriovenous oxygen difference, number of open capillaries, arteriolar and venular flow volume, and flow rate of red blood cells in the microvasculature [7, 8]. Therefore, BEMER can potentially be used in the treatment of neck pain by improving microcirculation in muscular tissue. Last year we have successfully utilized the BEMER therapy without any adverse effects in a prior study on low back pain.

F. Placebo

1. Placebo (Combined light touch and BEMER Sham): Treaters will place their hands lightly on the subject's cervical paraspinal muscles in the supine position in the same area as one would place their hands for cervical MFR, and on the subjects upper thoracic paraspinal muscles in the prone position in the same area as one would place their hands for thoracic MFR (approximately 5 minutes). However, no pressure or action will be done. In addition, the subject will lie down on the BEMER mat (as they would do during a BEMER session), but the device will not be activated. This treatment will be used as a control.

G. The research assistants will individually coordinate experimental times with the subjects. A licensed osteopathic physician will be in the vicinity of the treatment location at all times while treatments are being given.

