### **II. Costs**

A. Payment to subjects:

1. BEMER Pro Set: \$6410

2. 3 week compensation: \$50 per individual (estimating 40) = \$2,000

B. Total = \$8410

C. All paid by grants TBD

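### Efficacy could be read from before-after tests within each arm: the plan states no contrast with placebo and no rule for which test decides

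*Combined protocol and SAP*

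**What the plan says.** The whole statistical plan is in section III.A (Study Statistics) of the combined protocol and SAP.

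- Item 1 gives the primary outcome variable as "Questionnaire ratings before and after treatments". It then lists the Neck Disability Index (NDI), the SF-12 and the visual analogue scale (VAS) without ranking them.
- Item 2.a: "Paired T-tests (N~10 subjects) to investigate the changes in neck pain after each treatment protocol".
- Item 2.b: "One-Way ANOVA to investigate any statistically significant differences between the means of each of the 4 experimental groups".

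The arms are OMT, BEMER, OMT+BEMER and a combined sham. Section I.F (Placebo) says of the sham: "This treatment will be used as a control". The Research Purpose is to study the two treatments separately and together.

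On timing, section II.A.3.c says "Subjects will complete brief questionnaires regarding neck pain and quality of life before the beginning of study", with the same forms repeated after the three weeks. Inclusion covers faculty, staff and students "who are currently experiencing neck pain will be approached for recruitment", with no minimum duration or severity. The cost section budgets compensation for an estimated 40 subjects.

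No section gives a significance level, a contrast of any active arm with placebo, a contrast of the combination with its components, a post-hoc procedure, a multiplicity rule, or a statement of which analysis decides efficacy.

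**The concern.** Item 2.a is the only analysis that names neck pain and the only one that gives a result for a particular arm, yet it makes no use of the control. A change from before to after contains whatever would have happened anyway: recovery, placebo response and regression to the mean. Subjects enter because their neck hurts now, so some improvement over three weeks is plausible in every arm. Finding significance in an active arm but not in placebo is not a comparison of the two arms.

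Item 2.b does include placebo, but it leaves three gaps:

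- The means could be post-treatment scores or changes.
- A significant omnibus F does not say which arm differs from which. The obvious next step would be to look at the arm-by-arm paired tests, which is the invalid inference.
- Neither test isolates OMT or BEMER against placebo, or the combination against either component, although that is the stated purpose.

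At stake is the main conclusion: improvement shared by all arms could be reported as a treatment effect.

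**Working it through.** **Inputs from the documents.** There are four arms, one of them placebo. Item 2.a gives about 10 subjects and does not say whether that is per arm. The 40 budgeted subjects over 4 arms give 40/4 = 10, so I read it as 10 per arm with equal allocation. That is an inference. The figure of 10 cannot be derived further, because no alpha, power, effect size or SD is given.

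**Assumptions not in the documents.** Two-sided 0.05; no treatment effect; the same improvement in all four arms, d = 0.3, 0.5 or 0.8 SD of change; correlation 0.5 between questionnaires where more than one is tested.

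**Number of paired tests.** 4 arms × 1 outcome = 4 if neck pain means the VAS only; 4 × 2 = 8 with the NDI; 4 × 3 = 12 if the SF-12 is also tested. Section II.A.3.c names neck pain and quality of life separately, so 12 is the widest reading and the least supported.

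**Step 1: one arm, one outcome.** The paired t statistic follows a noncentral t with 9 df and noncentrality d√10. The chance p of a significant improvement is 0.134, 0.293 and 0.616 for d = 0.3, 0.5 and 0.8.

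**Step 2: any of the three active arms.** The chance is 1 − (1 − p)³ = 0.350, 0.646 and 0.943.

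**Step 3: some active arm significant and placebo not.** The chance is [1 − (1 − p)³](1 − p) = 0.30, 0.46 and 0.36. This is the pattern most easily mistaken for efficacy.

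**Step 4: several outcomes, and the ANOVA (simulation, 4 arms × 10).** Chance of a positive result when there is no treatment effect:

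| Reading | d = 0.3 | d = 0.5 | d = 0.8 |
|---|---|---|---|
| Paired tests alone, 1 outcome | 35% | 65% | 94% |
| Paired tests alone, 2 outcomes | 53% | 83% | 99% |
| Paired tests alone, 3 outcomes | 64% | 90% | >99% |
| Paired test and ANOVA of change both significant, 1 outcome | 4% | 4% | 5% |
| Both significant on the same outcome, any of 3 | 10% | 12% | 13% |

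The ANOVA of change alone is significant in 5%, 9% and 13% of trials for one, two and three outcomes, whatever the common improvement. The one-outcome rows do not depend on the correlation. For paired tests on three outcomes, a correlation of 0.2 gives 70/94/>99% and 0.8 gives 54/83/99%.

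**Step 5: no improvement at all.** A false improvement in some active arm occurs with probability 1 − 0.975³ = 7% on one outcome. It is 13% on two and 18% on three (1 − 0.975⁹ = 20% if the three were independent).

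**Step 6: what a direct contrast can deliver.** ANCOVA over four arms of 10 leaves 40 − 5 = 35 residual df. The 95% CI half-width for an active-minus-placebo difference is t(0.975, 35) × √(2/10) = 2.030 × 0.447 = 0.91 residual SD. The difference detectable with 80% power is 1.29 residual SD at 0.05, and 1.51 at 0.05/3. In simulation (baseline correlation 0.5, common shift 0.5 SD), the chance of any false active-versus-placebo finding is about 13% unadjusted, about 4% with Holm and about 5% with a fixed order.

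**The case against.** The strongest reply is that the plan already contains a comparison of all four randomised groups, placebo included, and that the literature review describes a controlled study. On that reading the ANOVA is the intended test and item 2.a merely looks at changes. If a claim needed both tests on one outcome, the error would be about 4 to 5%. This is fair as far as it goes: the large rates describe one permitted reading and are not the plan's error rate. But no rule selects the other reading, and even a significant ANOVA would not identify which arm beats placebo.

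Several narrower points also stand.

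- The three-outcome figures stretch item 2.a, which speaks of neck pain. The one- and two-outcome figures are the ones to rely on.
- A between-arm analysis of change would also be valid under randomisation. ANCOVA is preferred for precision and is not the only correct choice.
- Section III of Research Participants removes non-adherent subjects and those with adverse effects, so fewer than 10 per arm may be analysed. With 8 per arm the half-width becomes 2.052 × √(2/8) = 1.03 residual SD and the detectable difference 1.45.
- Placebo subjects receive both shams, while no sham of the other component is described for the single-treatment arms. Those contrasts therefore also reflect differing contact.

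The last two are separate design questions. They limit what the contrasts can show but do not make a within-arm test a substitute for them.

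**Conclusion.** The concern holds and must be fixed before the data are analysed. Two listed analyses can give opposite answers on the same data, and the plan does not say which one governs. Neither one, as written, isolates the effects that the study purpose names.

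If the paired tests are read on their own, a shared improvement of 0.5 SD of change would make at least one ineffective treatment look effective in about two trials in three on a single outcome, against 5% for the ANOVA of change. This figure rests on 10 analysed subjects per arm, two-sided 0.05 and the assumed size of the shared improvement. The finding that the plan lacks a decisive between-arm comparison rests on none of these assumptions; it follows from the text.

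**What to change.** Name one primary outcome, VAS or NDI at the sponsor's choice, and make the other questionnaires secondary. Replace items 2.a and 2.b as the efficacy analysis with wording such as:

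> The week-3 score will be analysed by ANCOVA over all four arms with the baseline score as covariate. Each active arm minus Placebo will be estimated with a 95% CI and tested at two-sided 0.05 with Holm adjustment over the three contrasts. OMT+BEMER minus OMT and OMT+BEMER minus BEMER will be estimated with 95% CIs as secondary comparisons. Within-arm changes will be reported as means with CIs, without p-values or conclusions on efficacy.

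A fixed testing order may replace Holm if the order is written into the plan before any outcome data are seen. If the combination is to support a formal claim, its two contrasts should join the same adjustment. If the ANOVA is kept, state its dependent variable and label it supportive. The analysis population should be named at the same time.

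The cost is plan wording only: baseline and week-3 scores are already collected and no subjects are added. The price is that significance is harder to reach. At 10 per arm only large differences are detectable, about 1.29 residual SD for the first test in a fixed order or 1.51 at Holm's first step. The report should therefore lead with estimates and intervals.

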Bio-Electro-Magnetic-Energy-Regulation (BEMER) therapy is a therapeutic modality that deploys a biorhythmically defined stimulus through a Pulsed Electromagnetic Field (PEMF), which leads to an increase in blood flow. The positive effects of BEMER on the circulation has been shown to result in significant increases in arteriovenous oxygen difference, number of open capillaries, arteriolar and venular flow volume, and flow rate of red blood cells in the microvasculature [7, 8]. Although there has not been any studies on the effects of BEMER on neck pain, BEMER with physiotherapy has shown reduction in pain and fatigue acutely in patients with chronic low back pain [9]. A systematic review of randomized controlled trials that investigated whether PEMF was effective in low back pain showed there was a decrease in pain intensity and improved functionality in individuals with different low back pain conditions [10]. By this mechanism, it is plausible that the combination of OMT and BEMER therapy may help increase circulation to myofascial structures that influence neck restriction and pain. With promising evidence, there remains ample opportunity to study treatment modalities and the use of complementary techniques and therapies combined with OMT [4, 6, 16]. The purpose of this study is to investigate the individual and combined effects of OMT and BEMER therapy on neck pain.

In summary, there is generally moderate and favorable evidence supporting the utility of OMT, and a growing body of evidence regarding BEMER therapy. However, plentiful literature also indicates the need for further exploration of these therapies individually as well as in combination, and their effect on neck pain. It is a goal of this project to further investigate the effects of individual and combined therapies in a controlled, single-blinded study.

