#### **C. Data Collection**

1. After written consent is obtained, the study coordinator will assign the participant a randomized study number to de-identify the participant.

2. To achieve our project's goal, we will have 4 separate groups (OMT, BEMER, OMT+BEMER, and Combined Placebo of OMT+ Sham BEMER). All treatments will be performed by osteopathic medical students. [name] will provide students

- additional training on OMT and placebo treatments, and [name], a BEMER representative, will provide additional training on BEMER treatments.
3. To control for anchoring bias, subjects will be randomized into one of the four groups: OMT, BEMER, OMT+BEMER, and Placebo.
- D. Osteopathic Manipulation Diagnosis and Treatment Protocol (OMT)
1. Osteopathic Diagnosis and Screening
    - a) Screening Special tests: Spurling's test, Wallenberg test
    - b) Observe and Palpate Cervical and Thoracic spine muscles for TART (tissue texture change, asymmetry, restriction of motion, and tenderness) changes- AROM and PROM of the cervical spine (using head and neck motion for T1-4)
    - c) OA (atlanto-occipital joint), AA (atlanto-axial joint), C2-C7 (cervical vertebrae 2-7), and T1-4 (thoracic vertebrae 1-4) intersegmental diagnosis
    - d) TMJ (temporomandibular joint) assessment – opening and closing of jaw
    - e) Counterstrain Tenderpoint screening for the following muscles: Medial pterygoid, Anterior C7, Anterior C8, Posterior C1 inion
    - f) 1st rib somatic dysfunction
  2. Osteopathic Manipulative Treatment/Techniques
    - a) Suboccipital Release (constant inhibitory pressure), supine – myofascial release/soft tissue technique
    - b) Contralateral Traction, supine - soft tissue technique
    - c) Upper thoracic spine unilateral prone pressure, prone - soft tissue technique
    - d) Direct or Indirect Thoracic inlet/outlet, supine – myofascial release technique
    - e) Occipitoatlantal somatic dysfunction muscle energy (post-isometric relaxation) supine
    - f) Atlantoaxial somatic dysfunction muscle energy technique (post-isometric relaxation) supine
    - g) C2-C7 somatic dysfunction muscle energy technique (post-isometric relaxation) supine
    - h) T1-4 Dysfunction muscle energy technique (post-isometric relaxation) - seated
    - i) 1st rib elevation dysfunction – articular technique – seated
    - j) Direct or indirect Sub mandibular release, supine - myofascial release technique

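### The only between-arm analysis is an omnibus one-way ANOVA on an unstated score, so the plan as written does not estimate the individual and combined effects that are the trial's aim

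*Combined protocol and SAP*

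**What the plan says.** The Research Purpose is to "investigate the individual and combined effects of Osteopathic Manipulative Treatment (OMT) and Bio Electro-Magnetic Energy Regulation (BEMER) Therapy on neck pain in adults", and the Review of Literature repeats the goal to "further investigate the effects of individual and combined therapies in a controlled, single-blinded study". Under Data Collection, "subjects will be randomized into one of the four groups: OMT, BEMER, OMT+BEMER, and Placebo". Of the combined light touch and sham BEMER, the Placebo item says: "This treatment will be used as a control".

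Section III.A (Study Statistics) gives the primary outcome as "Questionnaire ratings before and after treatments" and lists three instruments: the Neck Disability Index, the SF-12 and the visual analog scale. The statistical plan then has two lines. Item 2.a is paired t-tests of change after each treatment protocol, with about 10 subjects. Item 2.b is a "One-Way ANOVA to investigate any statistically significant differences between the means of each of the 4 experimental groups".

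The text does not say whether these means are week-3 scores or changes, or which instrument they come from. It names no contrast, reference arm, confidence interval, alpha, multiplicity rule or baseline covariate. Both sets of scores will exist: "Subjects will complete brief questionnaires regarding neck pain and quality of life before the beginning of study", and they "will complete the same questionnaires following the completion of the three week treatment".

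**The concern.** The aim poses specific questions: does OMT work, does BEMER work, and does the combination do better than either alone? Each is a difference between two named arms, and the plan commits to none of them. A significant F says only that some mean differs from some other.

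The paired t-tests do not fill the gap. Change within an arm mixes treatment effect with placebo response and natural recovery, and separating these is what the Placebo arm is for.

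Two things are at stake. Followed literally, the trial could report that the arms differ and still leave its own question unanswered. And because the score and the pairs are open, they could be chosen after the data are seen.

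**Working it through.** **Inputs from the documents.** There are four arms. About 10 subjects (item 2.a), read as per arm, gives 4 × 10 = 40, which matches the 40 participants estimated under Payment and Costs. The plan gives no alpha, power, effect size or SD, so it has no power figure to reproduce.

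**Assumed.** 10 per arm, equal allocation, no dropout, two-sided 0.05, a true difference of 0.8 SD, and a baseline-to-week-3 correlation r of 0.1 to 0.7, which the documents do not give.

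**1. What the F test can tell apart.** Noncentrality is 10 × Σ(mean − grand mean)², with 3 and 36 degrees of freedom.

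- One arm at 0.8 and three at 0: the grand mean is 0.2, and 10 × (0.6² + 3 × 0.2²) = 4.8. This holds whether the arm is OMT, BEMER or OMT+BEMER.
- All three active arms at 0.8 and Placebo at 0: the grand mean is 0.6, and 10 × (3 × 0.2² + 0.6²) = 4.8.

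All four patterns give 38% power and the same distribution of F. If OMT works wherever it is given, so that two arms sit at 0.8, noncentrality is 10 × 4 × 0.4² = 6.4 and power 50%. The same 6.4 arises if it is BEMER that works wherever given.

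A named contrast does separate such patterns. By simulation at r = 0.5 (40,000 runs), the baseline-adjusted OMT+BEMER minus OMT contrast is significant at 0.05 in 51% of trials if only the combination works, and in 5% if all active arms are equally effective.

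**2. What the open choices permit.** Simulated with no true effect, one instrument, r = 0.1 to 0.7; share of trials with at least one false pairwise difference:

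| How pairs are read | Score fixed in advance | Post or change score chosen afterwards |
|---|---|---|
| Only after a significant F | about 5% | about 9% |
| All six pairs, F ignored | about 20% | 31–34% |

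**3. Precision of one contrast, 10 against 10.** Noncentrality is 0.8² / (v × 2/10). The residual variance v is 1 on post scores, 2(1 − r) on change scores and 1 − r² with baseline adjustment. Error df are 36, or 35 with the covariate. On post scores 0.64 / 0.2 = 3.2. Adjusted at r = 0.5, 0.64 / (0.75 × 0.2) = 4.27.

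| r | Post score | Change score | Adjusted |
|---|---|---|---|
| 0.1 | 41% | 25% | 42% |
| 0.3 | 41% | 31% | 45% |
| 0.5 | 41% | 41% | 52% |
| 0.7 | 41% | 61% | 68% |

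The 95% interval for a post-score difference is about ±2.028 × √(2/10) = ±0.91 SD.

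**4. Check on the remedy.** With no true effect, at least one of five unadjusted 95% intervals excludes zero in about 17–18% of trials. Listing contrasts with ordinary intervals would therefore not control error by itself. Holm over the five tests brings any false rejection to about 4%.

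**The case against.** The one-way ANOVA is valid under randomization, and pairwise differences can be drawn from the same fit. Many readers would take post-hoc tests as implied. Outcome analyses are also to be blinded, which restrains favouring a treatment. These points stand in part: this is under-specification, not an invalid analysis. But implied tests leave the pairs, the score and the error control open, and blinding does not stop significant contrasts from being picked.

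A reader might infer that the plan carries a false-positive rate of 20% to 34%. The documents do not support that. Those figures apply only if the planned F test is ignored; used as a gate on one fixed score, it holds the rate at about 5% when no arm differs. Gating is not written into the plan either, so no single rate can be assigned to it.

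A reader might also infer that combination minus a single treatment would isolate the added component. It would not. Light touch and sham BEMER are described only for the Placebo arm, so the single-treatment arms also differ from the others in sham and contact exposure.

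Finally, adjusting for baseline gains almost nothing at r = 0.1. The case for naming the score and the contrasts does not depend on that gain.

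**Conclusion.** The point holds as one of analysis choice. Item 2.b is a valid global test that does not deliver the stated aim, and item 2.a cannot substitute for it. That conclusion rests on the text alone. It does not mean that the trial's data cannot answer the question: the same four arms and two questionnaire rounds would do so once the score and the comparisons are named.

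The sizes rest on the assumptions listed. They are somewhat optimistic, because subjects who do not adhere to the full regimen are to be removed from the study, which would shrink the arms. Even so, one contrast has only about 41% power on post scores and 42% to 68% adjusted, so estimates with intervals would be the most useful output, and none is planned. Grade: should-fix, a cheap improvement.

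**What to change.** Replace item 2.b with an ANCOVA of the week-3 score on baseline score and four-level arm. Then state:

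- **Outcome.** One questionnaire is primary (the sponsor's choice); the other two are secondary and outside the primary error control.
- **Contrasts.** OMT, BEMER and OMT+BEMER each minus Placebo, and OMT+BEMER minus OMT and minus BEMER, each as a difference with a 95% confidence interval.
- **Error control.** Holm over the five primary-outcome tests. Either give simultaneous intervals, or label the intervals as unadjusted and not to be used for significance claims.
- **Other tests.** The omnibus F may stay as a global test. The paired t-tests are descriptive and support no between-arm conclusion.
- **Interpretation.** The OMT-only and BEMER-only arms are not described as receiving the other component's sham, so contrasts involving them also reflect differences in sham and contact exposure.

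The cost is plan wording and one degree of freedom; no new data are needed. The drawback is power. If only the combination works (0.8 SD), Holm lowers the power of OMT+BEMER minus OMT from 51% to about 28% at r = 0.5 (simulated). Simultaneous intervals are also wider: Bonferroni over five gives about ±1.22 SD on post scores, against ±0.91 SD unadjusted.
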